(3) Loss of confidentiality: Confidentiality issues dominate concerns for the successful completion of this study. Subjects are asked to provide the participants/family members/neighbor's address, phone numbers: home number, work number, cell phone number; and email address. Participants may also be concerned about providing information on their demographics and smoking habits and the related lack of privacy. Special procedures will be put in place to assure that the data from the electronic questionnaires and follow-up questionnaires are kept secure and confidential. In addition, there is the potential for breach of confidentiality from the audio recorded sessions. In order to prevent this, no identifying information will be used in the audio recordings and the audio recordings will be destroyed at the end of the study.

(4) Nicotine withdrawal and NRT effects: If the participant quits using tobacco, he or she could experience withdrawal symptoms from nicotine cravings such as hunger, anxiety, restlessness, or sleep disturbance. Individuals who quit their addiction to tobacco products commonly experience these symptoms. If the subject uses NRT, they might experience a negative reaction. We will include a statement on the informed consent form warning of the possible side effects of NRT use, and the contraindications for use of NRT. NRT will never be dispensed without review of the caregiver's history by the PI and CRC. In addition, detailed information on the use of Nicotine Replacement Therapy (including contraindications for use) will be given to participants. Participants will be screened by the PI (a physician) or a trained CRC supervised by the PI for eligibility for NRT use. Participants receiving NRT will be instructed to call the PI if they encounter any questions, concerns or problems related to the NRT. The PI will be available via phone or in person to provide immediate, appropriate medical advice. If any adverse reactions or complications occur as a result of this study, we will contact the Institutional Review Board (IRB) Chairperson within five working days.

Pregnancy: Pregnant smokers, nursing mothers, or women attempting to become pregnant during the course of this study will be allowed to participate in the study, but will not receive nicotine patches or lozenges.

RISK-BENEFIT ASSESSMENT

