Caregivers who meet inclusion criteria will be approached by the CRC or investigator. Written informed consent will be obtained from the parent/legal guardian. Parents will be asked if they agree to have any of their child's leftover saliva stored indefinitely for future research. Parents will be asked to initial their consent for this part of the study in the consent form. Assent will be obtained from all children over age 10.

When child participants turn 18 years of age during the course of the study we will attempt to re-consent them until the participant has exceeded the window for the last data collection timepoint. When child participants turn 18 years of age after the study has been completed, we will send them a letter describing the study procedures and give them the option to have their samples that have been stripped of personal identifiers destroyed rather than saved for future research.

DATA SAFETY AND MONITORING PLAN

The DSM Board will consist of individuals with expertise in behavioral research and human subject protection.

The first meeting of the DSM Board for this project would occur shortly after recruitment begins. The first meeting would be devoted to reviewing study protocols, including plans for human subjects, and determining the frequency and content of interim data analyses (if warranted). Subsequent meetings would occur as determined by the DSMB at their first meeting, but will occur at least annually. During these subsequent meetings, the DSMB will evaluate various aspects of the trial, including progress, data quality, recruitment, etc. The DSMB, together with the IRB, will review the rates of adverse events and serious adverse events and provide recommendations to the PI for protocol revision or trial stopping. The PI will inform NIH of any significant action taken as a result of the DSMB finding.

Frequency of DSM Reviews

The Principal Investigator will monitor the data safety and efficacy of this trial on an on-going basis, implementing the Data and Safety Monitoring Plan (DSMP), and complying with the reporting requirements. The IRB or DSM Board may request more frequent reviews (based on reported Adverse Events or Serious Adverse Events or for other reasons), with which [name] will comply.

Collection and Reporting of AEs and SAEs

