For purposes of monitoring and reporting adverse events, the following NIH definitions will be used: "Adverse event (AE): Any untoward medical occurrence that may present itself during treatment or administration of an intervention, and which may or may not have a causal relationship with the treatment." "Serious adverse event (SAE): Any medical occurrence that results in death; is life-threatening; requires inpatient hospitalization or prolongation of existing hospitalization; creates persistent or significant disability/incapacity, or a congenital anomaly/birth defects."

We do NOT anticipate any SAEs to be reported as a result of participation in this study. If a subject experiences any AEs/SAEs as a result of this study, all study staff will be trained by the PI to report these events to their CRC or use the toll-free phone number to contact the PI or the IRB at CCHMC directly within 24 hours of report of the event. If an AE or SAE is reported to the CRC, the CRC must report the event to the PI within 24 hours of notification. Patients may report AEs or SAEs directly to CCHMC via a local phone number available in their copy of the consent form.

The PI will report any AEs/SAEs to the CCHMC IRB within 24 hours of receipt of report from any source. AEs and SAEs will be reviewed by the IRB and/or the DSMB in a timely manner (depending on the severity of the event). All AEs and SAEs will be reported to NIH at a minimum in the annual progress report, or within 24 hours depending on the severity of the event.

Reporting Mechanisms of AEs/SAEs to the IRB, FDA, and NIH

All study CRCs will be trained to report any adverse event regarding patients enrolled in the study. These events would include severe withdrawal symptoms, reaction to use of nicotine replacement products, severe illnesses or death (from any cause).

Study staff may contact the PI in person, or the IRB at CCHMC directly within 24 hours of report of the event. If an AE or SAE is reported to the CRC, the CRC must report the event to the PI within 24 hours of notification.

Caregivers may report AEs or SAEs to the PI either in person or using the local study number to contact the PI or IRB at CCHMC directly. The Principal Investigator will report any AEs/SAEs to the CCHMC IRB within 24 hours of receipt of report from the subject. AEs and SAEs will be reviewed by the IRB and/or the DSMB in a

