timely manner (depending on the severity of the event). All AEs and SAEs will be reported to NIH at a minimum in the annual progress report, or within 24 hours depending on the severity of the event.

Reporting Mechanisms of IRB Actions to NIH

Any IRB action that results in stopping or significantly altering the trial will immediately be reported (within 24 hours of notification) to NIH by the CCHMC IRB Administrator.

Report of Changes or Amendments to the Protocol

The Principal Investigator will report and seek approval of the CCHMC IRB for any changes to the study protocol. A significant alteration of the study protocol will be reported to NIH by the IRB Administrator immediately.

FDA Regulated Research

Nicotine, an FDA-approved drug, does not require an Investigation New Drug (IND) application with the FDA, as the use in the current research is consistent with currently approved indications by the FDA.

APPENDICES

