Appendix A: (Baseline Assessment): Intervention to Reduce SHSe

Appendix B: SBIRT Materials

Appendix C: HHC Materials

Appendix D: Caregiver Locator and Demographic Screener

Appendix E: Eligibility Screener

Appendix F: NRT Checklist and Receipt Documentation

Appendix G: Six Week Assessment

Appendix H: Six Month Assessment

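### The DSMB is to review adverse-event rates, but the protocol describes no scheduled AE question in either arm, and its one active instruction to call reaches only NRT recipients, who are in SBIRT

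*Combined protocol and SAP*

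**What the plan says.** The Data Safety and Monitoring Plan is complete on onward reporting: "All AEs and SAEs will be reported to NIH at a minimum in the annual progress report". It also gives AE rates a use. The DSMB, together with the IRB, "will review the rates of adverse events and serious adverse events" and advises the PI on protocol revision or stopping.

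Under Collection and Reporting of AEs and SAEs, an AE is defined whatever its cause, as an occurrence "which may or may not have a causal relationship with the treatment". The sentence that starts staff reporting is narrower: "If a subject experiences any AEs/SAEs as a result of this study". The participant routes are permissive. The first reads "Patients may report AEs or SAEs directly to CCHMC via a local phone number available in their copy of the consent form", and the section on reporting mechanisms adds "Caregivers may report AEs or SAEs to the PI either in person or using the local study number". Coordinators are trained to report any AE. The examples given are severe withdrawal symptoms, NRT reactions, severe illness and death from any cause. Nothing says that coordinators ask about them.

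One instruction is active. Item (4) of Possible Risks says "Participants receiving NRT will be instructed to call the PI if they encounter any questions, concerns or problems related to the NRT". NRT is a component of the SBIRT condition; the Healthy Habits Control (HHC) components contain none.

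The follow-up forms, such as "Appendix G: Six Week Assessment", are listed by title only.

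**The concern.** A rate is informative only if there is a defined way of finding the events. Here the forwarding of known events is specified closely, while the finding of them is left to whoever chooses to speak up. Every caregiver in both arms is contacted at 6 weeks and 6 months, so there are two natural occasions to ask, and the narrative uses neither.

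The events the protocol names can arise in both arms. The Analytic Plan expects that some controls may obtain NRT themselves. Possible Risks says that people who quit commonly have withdrawal symptoms, and the sample size section expects some HHC caregivers to quit. The described prompt nevertheless reaches only one arm.

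Two things are at stake. The level of caregiver AEs shown to the DSMB may be too low. If the DSMB looks at the arms side by side, part of any difference may reflect who was prompted, not who was harmed.

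**Working it through.** The plan gives no AE rate, capture rate or AE comparison, so there is no figure of its own to reproduce. The check is mainly of the text.

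**Step 1. Every described source of AE information**

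| Source (section) | Whom it covers | Asked or volunteered | Linked to AE reporting |
|---|---|---|---|
| Phone number in consent copy; report to the PI (AE sections) | Both arms | Volunteered | Yes |
| Coordinators report any AE (Reporting Mechanisms) | Both arms | They pass on what reaches them | Yes |
| Instruction to call the PI (Possible Risks, item 4) | Study NRT recipients, hence SBIRT; NRT matters only | Prompted, then volunteered | Not stated |
| 6-week NRT contact (SBIRT Condition, Assist) | Caregivers given NRT | Asked about receipt, use and wish for more, then re-screened for contraindications; no step on reactions | No |
| Table 1 and Follow-up Assessments | Both arms | No AE, side-effect or withdrawal item; the child's SHSe-related visits and hospitalizations appear at all three time points | No link stated |
| Chart extraction (Clinical and cost data) | Children; no arm restriction stated | Not dependent on volunteering | No link stated |
| Appendices F to I; consent pages | Not in the supplied text | Unknown | Unknown |

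For caregivers, who are the people using NRT and quitting, every described route that leads to AE reporting depends on someone raising the event. For children, hospitalizations are collected on schedule but not tied to AE or SAE reporting.

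**Step 2. Can the same events occur in HHC?** The planning rates for 6-month point prevalence are 6.3% in HHC and 12% in SBIRT. Applied to 375 per arm (750 / 2):

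- HHC: 375 × 0.063 = 23.6 abstainers
- SBIRT: 375 × 0.12 = 45.0 abstainers

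Quitting-related symptoms are thus possible in both arms. If the intervention works, a real arm difference in them is also possible. Unequal capture would be mixed with that difference.

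**Step 3. Scale, under assumptions not in the documents.** Let n = 375 per arm, t = true AE proportion (equal in both arms) and s = share captured. Expected recorded events = n × t × s. The apparent ratio is (n × t × s in SBIRT) / (n × t × s in HHC), which reduces to the ratio of the two capture shares.

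With t = 10% there are 375 × 0.10 = 37.5 true events per arm. With 30% captured in HHC, 37.5 × 0.30 = 11.25 are recorded there. The last column uses a normal approximation for two proportions, two-sided 5%.

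| SBIRT capture | SBIRT recorded | HHC recorded | Apparent ratio | Chance of p<0.05 if arms were compared |
|---|---|---|---|---|
| 30% | 37.5 × 0.30 = 11.25 | 11.25 | 1.00 | 5% |
| 40% | 37.5 × 0.40 = 15.0 | 11.25 | 1.33 | 11% |
| 50% | 37.5 × 0.50 = 18.75 | 11.25 | 1.67 | 29% |
| 60% | 37.5 × 0.60 = 22.5 | 11.25 | 2.00 | 51% |

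Across the same capture range, the last column runs from 5% to 28% at t = 5%, and from 5% to 95% at t = 30%.

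The top of the range is generous, because the instruction reaches only NRT recipients and only NRT matters. If a third of SBIRT events fell under it at 60% capture and the rest stayed at 30%, overall capture would be (1/3 × 0.60) + (2/3 × 0.30) = 0.40, which is the second row.

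On level alone, a true 10% would appear as 0.10 × 0.30 = 3% to 0.10 × 0.60 = 6%.

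**The case against.** The case on the other side is substantial, and most of it limits the point.

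- **Unseen forms.** The 6-week and 6-month assessments, both NRT checklists and the consent pages are not in the supplied text. An AE question or a general instruction to call may be there. A reader might infer that AEs are found only when volunteered; the documents do not establish that. They show that the protocol narrative describes no such question.
- **Table 1 is not exhaustive.** It omits caregiver carbon monoxide and cotinine, child urine and hand wipes, and the marijuana questions. Its silence on AEs is weak evidence alone. It carries weight because the follow-up description, the detailed account of the 6-week NRT contact and the AE section are silent too.
- **General routes cover both arms.** A reader might infer that only SBIRT caregivers are told how to report. In fact every participant has a number, may go to the PI, and is seen by coordinators trained to report any AE. The asymmetry is between an instruction and a permission, and it concerns NRT problems only.
- **No between-arm AE test is planned.** This stands, and makes a spurious significant result hypothetical. It does not help with incomplete capture, which affects the reviewed rates whether or not the arms are compared.
- **Second NRT supply.** It is tempting to say that it would be issued without anyone asking about the first. The re-screen uses a checklist whose content is unknown, with a study physician deciding if a contraindication appears. That inference is not supported.
- **Proportionality.** The study is proposed as minimal risk, uses an approved drug within its indications, and expects no study-related SAEs. Spontaneous reporting is a defensible choice, but it sits poorly with asking a board to act on rates.

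**Conclusion.** The point holds in a limited form. The plan relies on AE rates for oversight but describes no systematic way of finding caregiver AEs at follow-up. Its one active prompt applies to study NRT recipients, and so to SBIRT. Caregiver AE rates may be incomplete, and may be more fully ascertained in SBIRT.

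The stronger reading, that the rates are under-counted and cannot be compared between arms, is not demonstrated. Under-counting follows only if capture is below 100%, and bias between arms only if capture differs. The documents give neither. Any multiple, such as the 2.5-fold excess obtained by assuming 50% against 20% capture, merely restates the assumed capture ratio (0.50 / 0.20 = 2.5). The range of 1.0 to 2.0 shown here has the same status. It says that modest differences in capture could matter, not that they exist.

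The conclusion rests on the supplied text being the full narrative on AE collection. It would reduce to a cross-referencing gap if Appendices G to I already contain the questions.

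**What to change.** 1. Check Appendices G, H and I. If they already ask about AEs and NRT reactions in both arms, cite those items in the AE section and in Table 1.
2. If not, add one short, identical AE question set to the 6-week and 6-month assessments for all caregivers in both arms. Cover the events the protocol already names: severe withdrawal symptoms, NRT reaction and severe illness. At 6 weeks, ask it before the NRT re-screen. List it in Table 1 at T1 and T2. This changes data collection only, not any rule on who receives NRT.
3. Give the DSMB event counts by arm, with solicited and spontaneous events shown separately. Recruitment has begun: the compensation section describes an incentive added during the study, and participants consented before Version 11 may be re-consented. The counts should therefore also be split into periods before and after the change.
4. While amending, state whether child hospitalizations found on schedule or by chart review enter SAE reporting, and reconcile the cause-free AE definition with the narrower staff-reporting sentence.

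The cost is an IRB amendment, a few items at contacts already made, and more AEs to process under the existing reporting rules. There will also be two ascertainment periods that should not be pooled without comment.

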Appendix A: (Baseline Assessment): Intervention to Reduce SHSe

Appendix B: SBIRT Materials

Appendix C: HHC Materials

Appendix D: Caregiver Locator and Demographic Screener

Appendix E: Eligibility Screener

Appendix F: NRT Checklist and Receipt Documentation

Appendix G: Six Week Assessment

Appendix H: Six Month Assessment

